5.3 Safety Evaluations

1. Change from baseline QTc intervals and any clinically significant alterations in EKG after ^{18}F -fluciclovine PET/CT scanning
2. Change from baseline values in hematology and biochemistry profiles after ^{18}F -fluciclovine PET/CT scanning
3. Incidence of adverse events occurring after the ^{18}F -fluciclovine injection

6 SUBJECT SELECTION

6.1 Study Population

Eligible patients that meet inclusion and exclusion criteria will have suspicion of recurrent prostate carcinoma after presumed definitive therapy for primary disease.

6.2 Inclusion Criteria

1. History of histologically confirmed adenocarcinoma of the prostate post curative-intent local treatment (radical prostatectomy, local radiotherapy, brachytherapy)
2. Suspicion of recurrent prostate carcinoma after presumed definitive therapy for primary disease, defined as
 - a. Post-prostatectomy (with/without adjuvant RT): Detectable or rising PSA level that is ≥ 0.2 ng/mL with a second confirmatory level of ≥ 0.2 ng/mL
 - b. Post radiotherapy (without RP): PSA rise ≥ 2 ng/mL over nadir
3. Negative or equivocal findings on standard-of-care imaging for restaging of disease in the previous 60 days consisting of:
 - a. Whole-body $^{99\text{m}}\text{Tc}$ -MDP bone scintigraphy or NaF PET-CT (dependent on standard of care at the institution) and
 - b. Either CT or MRI of the pelvis (or the abdomen and pelvis).
4. Being considered for salvage therapy
5. Previous cryotherapy, external beam radiation, or HiFU must have occurred at least one year in the past.
6. Previous brachytherapy treatment will have occurred at least 2 years in the past

7. Ability to understand and the willingness to sign a written informed consent

6.3 Exclusion Criteria

1. Ongoing treatment with any systemic therapy intended for the treatment of prostate cancer (e.g., antiandrogen or LHRH agonist or antagonist)
2. Androgen deprivation therapy (ADT) in the past 3 months.
3. History of bilateral orchiectomy.
4. Inability to tolerate ^{18}F -fluciclovine PET/CT.

7 CONCURRENT MEDICATIONS

7.1 Allowed Medications and Treatments

All standard and approved treatments are permitted except for those specifically prohibited in section 7.2.

7.2 Prohibited Medications and Treatments

The following medications and treatments are prohibited prior to the ^{18}F -fluciclovine PET/CT. Any administration of ^{18}F -fluciclovine during treatment with these will be considered a protocol violation.

[figure not shown]
- Treatment with any systemic therapy intended for the treatment of prostate cancer (e.g., antiandrogen or LHRH agonist or antagonist)
- Bilateral orchiectomy

8 STUDY TREATMENTS

[figure not shown]
8.1 Formulation of Test Product

^{18}F -fluciclovine is a radiolabelled synthetic amino acid. The radioactive isotope ^{18}F decays with a half-life of approximately 110 minutes.

Chemical formula

Chemical structure

Chemical name

(anti)-1-amino-3-[¹⁸F]fluorocyclobutane-1-carboxylic acid.

Physiological effects

Biodistribution and radiation dosimetry studies have demonstrated physiological uptake of ¹⁸F-fluciclovine to be highest in the liver and pancreas, with rapid biological clearance. (9) There is low albeit prolonged uptake in skeletal muscle and bone marrow, with clearance dominated by the tracer half-life. (9)

8.2 Packaging and Labeling

The investigational agent is supplied as a unit dose for injection in a syringe with a radioactive concentration at a reference date and time that is stated on the container label. Each syringe is supplied in a container providing appropriate radiation shielding. Information will be provided with the shipment giving the confirmation number, radioactive concentration of injection (mCi/mL) at a stated time and date, shelf life information, protocol number and a unique prescription number. The radiochemical purity of ¹⁸F-fluciclovine injection is not less than 95% during the shelf life of the product

8.3 Supply of Study Drug at the Site

Sites will be provided with instructions for ordering the ¹⁸F-fluciclovine injections for use in the study. The order for a specific patient to be scanned at a specific date and time must be made to PETNET Solutions Centralized Scheduling Team ([contact]). The ¹⁸F-fluciclovine will be delivered from the radiopharmacy to the imaging site by courier. Each syringe is supplied in a container providing appropriate radiation shielding. The site must keep records of all shipments of ¹⁸F-fluciclovine received, dispensing and disposal/destruction performed on site as is appropriate to each facility.

8.4 Dispensing

When the study site receives the dose and prior to administration, the activity in the syringe will be measured in a dose calibrator. Should the activity be less than 8mCi or the volume required exceed 5 mL undiluted material or the administration be more than 10 hours from manufacture the scan should not be performed.

8.5 Administration Instructions

Prior to PET/CT, 10mCi \pm 20% of ¹⁸F-fluciclovine will be administered as an IV bolus injection followed by a 10 mL saline flush. ¹⁸F-fluciclovine will be injected through a cannula (or indwelling catheter) with the subject lying in a supine position and in an antecubital vein or another vein that will provide access. The administration site will be evaluated pre- and post- administration for any reaction (e.g. bleeding, hematoma, redness, or infection). Documentation of administration to a subject will be recorded according to standard of care and on the appropriate eCRF, including date, prescription number, total volume, start/stop time of administration, and injection site.

8.6 Study Drug Accountability

An accurate and current accounting of the dispensing and disposal of ¹⁸F-fluciclovine for each subject will be recorded on the Investigational Drug Accountability Record. The study monitor will verify this document throughout the course of the study.

9 STUDY PROCEDURES AND GUIDELINES

A Schedule of Events representing the required testing procedures to be performed for the duration of the study is diagrammed in Appendix 1.

Prior to conducting any study-related activities, written informed consent and the Health Insurance Portability and Accountability Act (HIPAA) authorization must be signed and dated by the subject.

9.1 Informed Consent

The participant must sign and date the local site IRB-approved version of the Informed Consent form before any study-specific procedures are performed.

Written and oral versions of the Participant Information and Informed Consent will be presented to the participants detailing no less than: the exact nature of the study; what it will involve for the participant; the implications and constraints of the protocol; the known side effects and any risks involved in taking part. It will be clearly stated that the participant is free to withdraw from the study at any time for any reason without prejudice to future care, and with no obligation to give the reason for withdrawal.

The participant will be allowed as much time as wished to consider the information, and the opportunity to question the Investigator, his referring physician or other independent parties to decide whether he will participate in the study. Written Informed Consent will then be obtained by means of the participant's dated signature and the dated signature of the person who presented and obtained the Informed Consent. The person who obtained the consent must be suitably qualified and experienced, trained in GCP and informed consent procedures. A copy of the signed Informed Consent will be given to the participant. The original signed form will be retained at the study site.

9.2 Clinical Assessments

Data from the following assessments and procedures should be documented in the Subject's medical records and recorded in the eCRF

1. Concomitant Medications

All concomitant medication and concurrent therapies will be documented at Screening and at all Visits and at End of Follow up. Dose, route, unit frequency of administration, and indication for administration and dates of medication will be captured.

2. Demographics

Demographic information will include age, gender, race and ethnicity.

3. Medical History

Include history of prostate cancer and prostate cancer treatments, and other clinically significant diagnoses. Prostate cancer history should include the date of initial diagnosis, initial tumor stage and Gleason score, dates of definitive therapy and adjuvant treatment (if given), and date of diagnosis of biochemical recurrence.

4. Imaging Studies

Imaging data will include all imaging results (including relevant bone scans, CT etc) from 60 days before screening so the final follow-up and all prostate cancer imaging results available from the Subject's file

5. Vital Signs

Blood pressure and pulse rate will be performed after resting for 5 minutes.

6. 12 lead Electrocardiogram (EKG)

EKG will be recorded as indicated in Section 10. Original EKGs are to be anonymized and forwarded to Clinical Research, Blue Earth Diagnostics, [name] and copies maintained in the Subject's medical record.

7. PSA Levels

PSA levels will be recorded from the Subjects medical records

8. Management Plan

The Intended Management Plan. The treating physician will complete the Management Plan Questionnaire to document his/her intended treatment including planned radiation fields, intended resection limits of surgery, use of brachytherapy, cryotherapy or HiFU, intended use of adjuvant therapy.

The Revised Management Plan. Where an additional diagnostic procedure (e.g., imaging or biopsy) is performed in light of the PET/CT findings, the results of these should be considered prior to recording the revised management plan. Any such diagnostic procedures do not qualify as a "change" to clinical management. The treating physician will complete the Management Plan Questionnaire to document changes to the Pre-scan Management Plan. Changes include such responses as change to radiation or surgical fields. The patient may enter another clinical trial as part of the Revised Management Plan.

Actual Management Plan. At the final follow up visit any deviations or changes to the Revised Management Plan will be documented

9. Biopsy

Biopsy is not required by the protocol; however patients with PET/CT positive findings in soft-tissue supported by anatomical abnormalities on CT or MRI may have a biopsy performed per standard practice where the procedure is deemed clinically feasible and safe. Biopsies completed within 4 months after imaging will contribute to the aim of the study.

1. Biopsy results of suspected bone metastases conducted per standard practice will also be collected. Bone lesions may be followed up through imaging where biopsy is not practical.
2. Based on local-radiologist/nuclear medicine physicians assessment of ¹⁸F-fluciclovine PET/CT-positive findings supported by anatomic abnormalities, conduct imaging-guided biopsy of soft-tissue ¹⁸F-fluciclovine -enhancement region per institutional standard of care;
3. Submit pathology report(s) to the ACR Core Laboratory. The address is given in the Imaging Manual.

10. Blood Chemistry Profile

Blood will be obtained and sent to each site's clinical chemistry lab for determination of serum sodium, potassium, calcium, chloride, BUN, creatinine, glutamic oxaloacetic transaminase (SGOT/AST), glutamic-pyruvic transaminase (SGPT/ALT), alkaline phosphatase, creatine kinase (CK), lactate dehydrogenase (LDH), albumin, total protein, total bilirubin.

11. Hematology

Blood will be obtained and sent to each site's clinical hematology lab for a complete blood count (hemoglobin, hematocrit, red blood cell count, white blood cell count, white blood cell differential, and platelet count determinations).

12. Urinalysis

Prior to the ¹⁸F-fluciclovine dosing a midstream sample of urine will be obtained and tested by dipstick for leukocytes, nitrite, pH, protein, ketones, glucose, bilirubin, urobilinogen, and blood. This will not be repeated following scanning unless clinically indicated.

13. Adverse Events

See Section 12.

10 EVALUATIONS BY VISIT

A Schedule of Events representing the required testing procedures to be performed for the duration of the study is given in Appendix 1

10.1 Visit 1 - Screening

1. Review the study with the subject and obtain written informed consent and HIPAA authorization
2. Record demographics data and current medication being taken.
3. Obtain medical history including treatment history.
4. Confirm negative or equivocal findings on baseline imaging studies (note: baseline imaging studies must be within 60 days prior Visit 1).
5. Measure vital signs
6. Obtain blood sample for:
 - PSA testing
 - Hematology
 - Biochemistry evaluations
7. Obtain 12-lead EKG
8. Obtain urine sample for dipstick urinalysis (may be collected and tested at any time between screening and the scan date)

10.2 Enrollment and PET/CT Preparation

Subjects who have provided informed consent and who meet all eligibility criteria will be enrolled into the study. At the time the Subject is determined to be eligible, the following activities will be performed:

1. Register the Subject via eCRF
2. Schedule the ¹⁸F-fluciclovine PET/CT imaging study within 30 days of Visit 1
3. The treating physician must complete the Management Plan Questionnaire. A copy of the Questionnaire must be maintained in the Subject's medical record.
4. PET/CT Preparation:

Subjects will be required to fast for at least 4 hours prior to the scan, drinking only sips of water within 4 hours of the scan if needed for administration of medications and not exercise from the day before the scan through to the time of the scan. Optionally, if it is the standard practice at the site, one hour prior to scanning, the patient may drink 500 mL of oral contrast (e.g. 1.2%, Read-Cat) over 1 hour to maximize conspicuity of abdomen and pelvic structures. No IV CT contrast will be used.

10.3 Visit 2 – ¹⁸F-fluciclovine PET-CT

Prior to the dose of ¹⁸F-fluciclovine and the PET/CT scan, the following assessments will be performed:

1. Review and update the Subject's medical history to check for new health-related events and changes to concomitant medications since the Screening visit.
2. Ensure treatment plan has been documented prior to ¹⁸F-fluciclovine PET/CT;
3. Obtain vital signs.
4. Obtain blood sample for:)
 - o Hematology)
 - Biochemistry) Unless obtained at screening
5. 12-lead EKG)
6. Obtain a urine sample and perform dipstick analysis.)
 - o If the results are abnormal these are to be recorded and the Subject is to proceed to having the fluciclovine PET/CT

Dosing and PET/CT Procedure: A venous cannula will be inserted and the Subject will receive one dose of ¹⁸F-fluciclovine. Subjects will be imaged starting 4 minutes after injection from proximal-thigh to skull base. The duration of the scan is approximately 25 minutes on the PET/CT scanner.

Following the scan, Subjects will be encouraged to drink water to encourage hydration and frequent voiding to reduce radiation dose from ¹⁸F-fluciclovine excretion. The following assessments will be performed

1. Obtain blood sample for:)
 - a. Hematology)
 - b. Biochemistry) Unless to be obtained in the next 7 days
2. 12-lead EKG)
3. Obtain vital signs immediately post scan and at 60 (± 5) minutes, and 120 (±5) minutes post-injection.
4. Assess the Subject for adverse events at 30 minutes, 60 minutes, and 120 minutes post-injection.

10.4 Visit 3 - Telephone Consultation at 24 - 72 (+/- 4) hours after dosing

An adverse event evaluation will be performed at **24 - 72 hours** (± 4 hours) after ¹⁸F-fluciclovine administration via telephone consultation.

10.5 Documentation of Management plan revision post ¹⁸F-fluciclovine PET/CT Scan (2-22 days following the scan)

The treating physician will complete the Management Plan Questionnaire to document changes to the Pre-Scan Management Plan. A copy of the Questionnaire must be maintained in the Subject's medical record.

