3 STUDY OBJECTIVES

3.1 Primary Objective

The primary objective is to measure the fraction of patients for whom ^{18}F -fluciclovine PET/CT alters patient treatment through detection of disease after curative-intent treatment in a population of men with elevated PSA levels indicative of persistent or recurrent prostate cancer and negative or equivocal findings on standard-of-care diagnostic imaging tests.

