Appendix 1: Schedule of Events

	Visit 1 - Screen up to 30 days before Visit 2	Document Initial Management Plan	Visit 2 - Day of ¹⁸ F-fluciclovine PET/CT				Visit 3	Document Post 18F-Fluciclovine PET/CT Management Plan	End of Study
			Pre-dose/pre-scan	Immed. post scan	60 min post dose	120 min post dose			
Study Day	-30 to Visit 2	Prior to Visit 2	1				2	2-22	180 ± 28 days
Visit Location/Type	Treating Physician Office	NA	PET/CT Imaging Center				Phone Call	NA	NA
Assessments/Procedures									
Informed consent	X								
Inclusion/ exclusion criteria	X		X						
Medical history	X		X						
PCa history, including treatment	X								
Record PSA levels ¹	X								X
Record imaging studies ²	X								X
Vital signs (heart rate and blood pressure)	X		X	X	X	X			
Height, weight			X						
Serum chemistry and hematology	X			X ³					
Serum PSA	X								
Urinalysis, dipstick	X ⁴								
EKG			X	X ³					
Record biopsy results, if applicable									X
Injection site assessment			X	X	X	X	X		
AE assessment				X	X	X	X		X
Concomitant medication assessment	X		X						X
Document management/plan		Plan						Revised	Actual
Treatment response assessment									X

1 - Record all available PSA levels obtained prior to Visit 1 through End of Study; for non-prostatectomy subjects, the PSA nadir and 2 times over nadir result must be documented in the record.

2 - Record all available imaging studies performed prior to Visit 1 through End of Study; negative or equivocal imaging within 60 days of Visit 1.

3 - Post-dose blood tests and EKG may be performed at the Imaging Center or within 7 days of the scan at another laboratory/site. *May be collected and tested at any time between screening and scan date

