5.4 Statistical Analysis

5.4.1 Primary Efficacy Analysis

The primary efficacy analysis will be based on the EAS and will be repeated on the PPS as a secondary analysis. Comparisons between the original treatment plan and the revised treatment plan will be categorised as no change, major change or other change. The definitions of the change categories are listed below.

- No change: the original treatment plan is the same as the revised treatment plan
- Major change: the original treatment plan is not the same as the revised treatment plan and the grouping for the original treatment plan is not the same as the grouping for the revised treatment plan

These will be further split and presented according to the following categories:

- Salvage or Non-curative systemic therapy to Watchful waiting
 - Salvage therapy to Non-curative systemic therapy
 - Non-curative systemic therapy to Salvage therapy
 - Alternative Major change
- Other change: the original treatment plan is not the same as the revised treatment plan but the grouping for the original treatment plan is the same as the grouping for the revised treatment plan

These will be further split and presented according to the following categories:

- Modified RT field plan
- Modified androgen-deprivation regimen
- Alternative Other change

Groupings of treatment plans are detailed in the following table:

Original Treatment Plan	Grouping for Original Tx Plan	Revised Treatment Plan	Grouping for Revised Tx Plan
Was androgen deprivation therapy planned	Androgen Deprivation Therapy	Androgen deprivation therapy	Androgen deprivation therapy
		Active surveillance	Active surveillance
		Chemotherapy	Chemotherapy
Salvage radiotherapy to the prostate bed	Salvage Radiotherapy	Salvage radiotherapy to the prostate bed	Salvage Radiotherapy
Salvage radiotherapy to the prostate bed, with boost to areas guided by conventional imaging		Salvage radiotherapy to the prostate bed, with boost to areas guided by conventional imaging	
		Salvage radiotherapy to the prostate bed with boost to areas guided by fluciclovine (18F) PET/CT	
Salvage radiotherapy to the prostate bed and whole pelvis	Salvage Radiotherapy	Salvage radiotherapy to the prostate bed and whole pelvis	Salvage Radiotherapy

Original Treatment Plan	Grouping for Original Tx Plan	Revised Treatment Plan	Grouping for Revised Tx Plan

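### The pre-scan plan is not confirmed near the scan and any later difference counts as a change, so plan changes unrelated to PET/CT can raise the primary fraction by an unknown amount

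*Protocol*

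**What the plan says.** **Timing of the intended plan.** Protocol 10.2 opens its list of steps with "At the time the Subject is determined to be eligible, the following activities will be performed". Among them are the treating physician's Management Plan Questionnaire and scheduling of the "PET/CT imaging study within 30 days of Visit 1". Appendix 1 gives the same window ("Visit 1 - Screen up to 30 days before Visit 2") and asks only that the initial plan exist before Visit 2.

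**Scan day.** Before dosing, Protocol 10.3 has the site "check for new health-related events and changes to concomitant medications since the Screening visit". For the plan, item 2 says only "Ensure treatment plan has been documented prior to" the scan.

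**Revised plan.** Protocol 10.5 places it 2 to 22 days after the scan. Appendix 1 shows study days 2 to 22, with the scan on day 1.

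**Counting rule.** SAP 5.4.1 defines "No change: the original treatment plan is the same as the revised treatment plan". Every other pair is a major or other change. No criterion refers to the cause. The evaluable set (SAP 4.1) needs both forms and sets no limit on the time between them.

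**Objective.** Protocol 3.1 asks for the fraction in whom the scan "alters patient treatment through detection of disease after curative-intent treatment". The synopsis and SAP 3.1 refer to intended management instead, but keep the same causal link to detection.

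**The concern.** The objective is causal, while the counting rule compares two dated forms. There is no control arm, and neither document gives a rate at which plans change without a scan. Protection against counting ordinary changes of plan therefore rests on a comparator that is current at the time of the scan and on some record of why the plan changed. The protocol expects that health events may arise between Visit 1 and the scan, because it reviews them on scan day, but it does not carry them into the plan that serves as comparator. A new diagnosis, a specialist consultation or a change in the patient's preference would then be scored in the same way as a change prompted by the scan. The study is sized for precision alone, and an exact binomial interval does not reflect a bias of this kind.

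**Working it through.** **1. Longest interval between the forms, within the stated windows**
- Text of Protocol 10.2 and 10.5: 30 + 22 = 52 days.
- Appendix 1 (scan on day 1, last day 22): 30 + 21 = 51 days.
- Both are ceilings. Appendix 1 allows the plan to be written at any time before Visit 2, so the interval can be much shorter.

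**2. The plan's own precision figure**
Protocol 14.4 and SAP 3.4 assume that 30% of positive scans change the plan and require 89 positive patients. Clopper-Pearson limits with x = 0.30 × 89 are 0.2074 and 0.4064, a width of 0.199. This agrees with the stated 0.207 to 0.406. The planned half-width is 10 points.

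**3. Effect of unrelated change**
Let p = 0.30 be the true PET-driven fraction and D the probability of an unrelated plan change between the two forms. D is an assumption, because the documents give no value. If the two are independent and an unrelated change never cancels a PET-driven one:

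observed = 1 − (1 − p)(1 − D), so bias = (1 − p) × D = 0.70 × D.

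| Assumed D | Observed | Bias (points) | Probability that the exact 95% CI (n = 89) covers 30% |
|---|---|---|---|
| 0% | 30.0% | 0 | 96.3% |
| 2% | 31.4% | 1.4 | 94.9% |
| 5% | 33.5% | 3.5 | 89.6% |
| 10% | 37.0% | 7.0 | 71.6% |

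A bias equal to the 10-point half-width needs D = 0.10 / 0.70 = 14.3%.

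**4. How much of this the timing of the plan controls**
Take an assumed unrelated-change rate m per 30 days, so that D = 1 − (1 − m)^(t/30). Compare t = 52 days with t = 22 days, the maximum if the plan is confirmed on scan day.

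| Assumed m | Observed, 52 days | Observed, 22 days |
|---|---|---|
| 1% | 31.2% | 30.5% |
| 2% | 32.4% | 31.0% |
| 5% | 36.0% | 32.6% |
| 10% | 41.7% | 35.2% |

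Confirmation on scan day removes 30 / 52 = 58% of the longest window. The days after the scan remain, and only a recorded reason for the change can deal with those.

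**5. Direction**
Under an any-difference rule, unrelated change adds to the numerator unless it happens to reverse a PET-driven change. The error therefore runs mainly upward.

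**The case against.** The protocol does not leave attribution out. Sections 2 and 4.1, and SAP 3.2, say that site clinicians document treatment changes arising from their review of the scan. Section 11.5 bases the revised decision on the nuclear medicine report. Section 9.2 item 8 excludes additional diagnostic procedures from counting as change. In the SAP 5.4.1 table, several revised-plan options name fluciclovine: guided boosts; guided cryotherapy, brachytherapy and HIFU; targeted resection; and targeted salvage treatment. A change recorded under one of these identifies its cause. The questionnaire itself is not in the documents and may already ask for a reason. SAP 5.4.1 also leaves the classification of change to be agreed before database lock.

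All of this stands, and it narrows the point. It does not settle the other changes, such as a move to androgen deprivation, to surveillance, or from prostate-bed to whole-pelvis fields. For these, SAP 5.4.1 compares the two plans and nothing more, and the classification to be agreed is described by type of change, not by cause. Nor can the scan-negative subgroup supply a background rate, because Protocol 2 expects a negative scan to influence management too.

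A reader might infer more than the documents support:
- **That the primary fraction is inflated.** No drift rate is given. At 1% to 2% per 30 days the bias is 1.2 to 2.4 points even at the longest interval.
- **That rising PSA drives the drift.** The only scheduled PSA draw is at screening. Later values are abstracted from records.
- **That the SAP's 6-month table carries the same bias.** SAP 5.4.2.1 compares actual management with the revised plan, so an outdated intended plan does not enter it. The point reaches only the intended-versus-actual comparison in Protocol 5.2 and 14.2 and SAP 5.2.

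**Conclusion.** The gap is real, and its size cannot be determined from the documents. The comparator for the primary endpoint can be up to 30 days old at the scan without being confirmed, and the counting rule ignores cause, so unrelated changes can enter the primary fraction. Across the assumed total of 2% to 10% unrelated change, the bias is 1.4 to 7.0 points: small beside the planned half-width at the low end, and enough to bring coverage down to about 72% at the high end. These figures rest on the 30% planning value, on independence, and on no cancelling changes. The sample size is not affected. The point merits a change because the remedy is cheap and the reasons for change cannot be recovered reliably after database lock, not because a bias has been shown.

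**What to change.** 1. **Protocol 10.3, item 2.** Have the treating physician confirm or update the intended plan, and date it, shortly before dosing, taking account of the Visit 1 PSA and any new events. Use that version as the comparator. Appendix 1 places Visit 2 at the imaging center, so allow this to be done remotely.
2. **Revised questionnaire.** Record, if the form does not already do so, whether each change was due to the PET/CT result or to another reason.
3. **SAP 5.4.1.** Keep the any-difference comparison as primary. Pre-specify a sensitivity analysis that counts only PET-attributed changes, and report the distribution of the interval between the two forms.
4. **Window wording.** Reconcile the one-day difference between Protocol 10.5 and Appendix 1.

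The cost is one short confirmation by the physician, a questionnaire item or two, one repeat table and a summary of intervals. No visit or procedure is added. The drawback is that attribution is reported by an unblinded physician, who may over-credit the scan. For that reason it belongs in a sensitivity analysis and should not replace the primary result.

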6.4 Electrocardiography

Electrocardiogram (EKG) interpretation is recorded pre-dose/pre-scan and within 7 days of the scan. EKG observed QTc and change from baseline will be summarised by visit. In addition, a summary of the incidence of outliers in absolute QTc intervals (>450 , >480 and >500 msec), and the change from baseline in QTc intervals (>30 and >60 msec both positive and negative changes) will be presented.

The overall interpretation of the EKG (Normal, Abnormal NCS, and Abnormal CS) will also be summarised by visit. All EKG results will be listed, including overall interpretation and change from baseline.

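### Section 10 lets a screening EKG replace the pre-dose EKG that Appendix 1 schedules on the scan day, so the QTc baseline may be anywhere from 0 to 30 days old

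*Protocol*

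**What the plan says.** **Protocol, Section 10.** The screening list in 10.1 includes, as item 7 and without condition, "Obtain 12-lead EKG". The pre-dose list in 10.3 marks the blood sample, hematology, biochemistry, EKG and urine lines with a closing bracket, and beside that bracket stands "Biochemistry) Unless obtained at screening". The post-scan list in 10.3 has the same layout, with "Biochemistry) Unless to be obtained in the next 7 days". Section 10.2 asks for the "PET/CT imaging study within 30 days of Visit 1".

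**Protocol, Appendix 1.** The first column is headed "Visit 1 - Screen up to 30 days before Visit 2". The EKG row is empty there. It has an unfootnoted mark in the Visit 2 column "Pre-dose/pre-scan" and a footnoted mark immediately after the scan. The footnote reads "Post-dose blood tests and EKG may be performed at the Imaging Center or within 7 days of the scan".

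**Which text governs.** Section 9.2 item 6 sends EKG timing to Section 10. The openings of Sections 9 and 10 describe the Appendix 1 schedule as the required testing.

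**SAP.** Section 3.3 takes visits and assessments from Appendix 1. Section 6 defines the ECG baseline as the last measurement before administration, counting the day of administration if there is one. Section 6.4 says the EKG "interpretation is recorded pre-dose/pre-scan and within 7 days of the scan". It summarises QTc and its change by visit, and counts changes beyond 30 and 60 msec in both directions.

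**The concern.** QTc change from baseline is the first safety evaluation listed in protocol 5.3. Because 10.1 gives everyone a screening EKG, the exemption in 10.3 is open to everyone. A site that works from Section 10 need record no EKG on the scan day before injection, while a site that works from Appendix 1 must record one.

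Two things follow. Where the screening value serves as baseline, the change includes whatever happened to the subject between screening and the scan. The protocol expects that something may happen, since 10.3 item 1 asks for new health events and medication changes since screening. Also, baselines of different age would be pooled without distinction. SAP section 6 presents safety tables by centre, so a difference in how centres read the protocol could look like a difference between centres. With no control arm, nothing in the data separates background change from an effect of the injection.

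**Working it through.** The plan states no figure for baseline age, so there is none to reproduce. The check is a comparison of texts and an addition of the stated windows.

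**1. Does the 10.3 exemption reach the EKG?** The EKG is item 5, between the blood sample (item 4) and the urine dipstick (item 6), and its line carries the same closing bracket as theirs. The post-scan list is laid out in the same way, and the Appendix 1 footnote confirms that the post-scan bracket covers both blood tests and EKG. The natural reading is that the pre-dose bracket does too.

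**2. Is the mismatch specific to the EKG?** Yes. For serum chemistry and hematology, Appendix 1 has a mark at Visit 1 and none pre-dose, which agrees with Section 10. For the EKG the pattern is the opposite.

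| | EKG at Visit 1 | EKG at Visit 2 before dose |
|---|---|---|
| Sections 10.1 and 10.3 | ordered for all | excused if done at screening |
| Appendix 1 | none | scheduled, no exemption |

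**3. Age of the baseline at dosing.** The inputs are a screening-to-scan interval of at most 30 days (10.2 and Appendix 1) and the SAP rule of the last value before administration.
- Section 10, with no Visit 2 pre-dose EKG: 0 to 30 days.
- Appendix 1: 0 days.

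**4. Time between the two EKGs.** Interval = age of baseline at dosing + delay of the post-dose EKG. The delay is 0 to 7 days (10.3, Appendix 1 footnote, SAP 6.4).

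| Post-dose EKG | Section 10 | Appendix 1 |
|---|---|---|
| On the scan day | 0 to 30 days | 0 days |
| 7 days after the scan | 7 to 37 days (maximum 30 + 7) | 7 days (0 + 7) |

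The maxima are 37 and 7 days.

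**5. Which outputs are affected?** Observed change = effect of the dose + background change over the interval. The baseline enters the mean change and the counts beyond 30 and 60 msec. It does not enter the post-dose counts above 450, 480 and 500 msec, which use the absolute value. In the by-visit summary, the pre-dose value would appear under screening for some subjects and under Visit 2 for others.

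**6. Can the effect be put in msec or outliers?** No. That needs the standard deviation of QTc change with no drug effect at each interval, and neither document gives one.

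**The case against.** The strongest reply is that this is a drafting mismatch in a descriptive endpoint. No hypothesis test, stopping rule or sample size depends on QTc. All EKG results and all medications are listed, so an odd change can be looked into. Without a control arm, background change cannot be separated from a dose effect under either schedule. The reach of the exemption is also inferred from bracket layout. All of this stands as a limit on the importance of the point. It does not remove the conflict between Section 10 and Appendix 1, and the documents set no precedence between them.

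Three stronger readings are tempting and are not supported:
- **That QTc change will be measured from a 30-day-old baseline.** Thirty days is a maximum. A site may follow Appendix 1, or record a Visit 2 EKG anyway, and the SAP rule would then use that value. An old baseline is permitted, not certain.
- **That Section 10 plainly contradicts SAP 6.4.** A screening EKG is literally recorded before the dose, and the SAP section 6 rule allows for a baseline from before the scan day. The tension with 6.4 comes only from its use of the name of the Appendix 1 Visit 2 column, together with SAP 3.3. The direct conflict is with Appendix 1.
- **That a number of spurious outliers can be stated.** Any such count would rest on assumed standard deviations. Setting a same-day value against an old-baseline value would also ignore that the post-dose EKG may come up to 7 days later even under Appendix 1. Nothing in the documents shows how far QTc variation grows between 7 and 37 days.

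**Conclusion.** The point holds as a minor internal inconsistency. Sections 10.1 and 10.3 allow the screening EKG to stand in for the pre-dose one, Appendix 1 does not, and the SAP baseline rule takes whichever value exists. Its size, as far as the documents go, is a baseline 0 to 30 days old instead of one from the scan day, and a maximum of 37 instead of 7 days between the two EKGs. The result is avoidable background variation and baselines that are not comparable in the QTc change summaries. The amount in msec or in outlier counts is unknown.

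The conclusion rests on reading the 10.3 bracket as covering the EKG and on some sites following Section 10, to which Section 9.2 directs them. The primary endpoint is not affected.

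**What to change.** Reconcile 10.1 and 10.3 with Appendix 1. Take the EKG out of the group that 10.3 excuses after screening, so that it is recorded at Visit 2 before injection, as Appendix 1 already schedules. State in the same amendment whether the screening EKG in 10.1 stays, and make Appendix 1 agree. If it stays, the SAP baseline rule needs no change, because the Visit 2 value is the later one.

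For subjects already enrolled, add to SAP 6.4 a split of the QTc change summaries, including the counts beyond 30 and 60 msec, by scan-day versus earlier baseline.

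The cost is protocol wording and one extra table split. If the screening EKG is dropped, the number of EKGs per subject does not rise above what Section 10 now asks; if it is kept, there is one more. The practical downside is that the imaging centre must have an EKG available before injection. Appendix 1 already assumes this, although its footnote, which allows the post-dose EKG to be done elsewhere, suggests that access may be limited at some centres.
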